1.4	October 7, 2025	[name]	-Clarified the tricep as measure for secondary skinfold thickness outcome -Refined definition of three adherence / consumption measures -Specified 'any' hospitalization as binomial secondary outcome (non-repeated)

2 Introduction

2.1 Background and Rationale

There is limited evidence on the management of moderate malnutrition (MAM) among children. While there is clear guidance on the management of children with severe wasting, there is currently no consistent guidance on how best to manage children with moderate wasting. While there is no consistent guidance on the management of moderate wasting in children and more evidence is needed, there is increasing recognition that treatment should be offered to those at the highest risk of death and deterioration, as children with moderate wasting and additional risk factors (e.g., infections) have higher risks of morbidity and mortality.

Moderate wasting is associated with a 3-fold higher risk of mortality in children under 5 years of age compared with their well-nourished peers. These deaths largely occur from infectious illnesses. The interactions between episodic infections and malnutrition are complex and bidirectional. Recent studies have elucidated possible mechanisms by which malnourished children are rendered more vulnerable to infection. And how an infection in turn worsens moderate wasting, resulting in deterioration to severe wasting and ultimately death. Acute infectious illness is a clear risk factor increasing the risk of adverse outcomes in moderately wasted children.

Despite mechanistic work in this area, there are no clinical trials that have been done in this high-risk subgroup to investigate if it is possible to break the malnutrition-infection cycle and decrease the risk of deterioration/death by initiating interventions targeting the nutritional (anthropometric) deficit. The NUTRIMAM trial proposes to evaluate different nutritional supplements in young children who are moderately wasted and present with an acute infection. The current IMCI guidelines on the feeding of moderately wasted children presenting to a health facility with illness recommend counseling on increased feeding using home-available foods. The Essential Nutrition Actions document (2013) recommends the provision of an increased amount of food after an acute illness. The findings from the NUTRIMAM trial are expected to fill in the gaps concerning guidance on the feeding of moderately wasted children with acute illness.

2.2 Objectives

The NUTRI-MAM trial will aim to evaluate the efficacy of locally available foods (LAF) or microbiota-directed supplementary food (MDSF) compared to ready-to-use supplemental foods (RUSF) when given to moderately wasted children presenting to health facilities with an acute illness, on initial anthropometric recovery (within 12 weeks of enrolment) and sustained recovery (at 24 weeks after enrolment).

Objectives

1. To determine the effect of (a) Locally Available Foods (LAF) compared to Ready to Use Supplementary Food (RUSF) and (b) microbiota-directed supplementary food (MDSF) compared to RUSF when given to moderately wasted children aged 6-24 months presenting to a health facility with an acute illness, on anthropometric recovery within 12 weeks of enrolment.

- 2. To determine the effects of (a) LAF compared to RUSF and (b) MDSF compared to RUSF, on sustained anthropometric recovery at 24 weeks after enrolment.
- 3. To determine the effect of a sustained recovery intervention compared with standard care (national standard of care following recovery) on sustained anthropometric recovery at 24 weeks after enrolment in the study.

3 Study Methods

3.1 Trial Design

NUTRI-MAM is a multi-center, open-label, sequential multiple assignment randomized trial that will be implemented in 5 countries - three in Asia (Bangladesh, India, and Pakistan) and two in Africa (Mali and Tanzania). The trial is a Sequential Multiple Assignment Randomized Trial (SMART) with two randomization stages. The first randomization stage occurs at enrollment and during 'Phase 1'. The second randomization stage occurs after 12 weeks and is referred to as 'Phase 2'. In Phase 2, only children who reached the anthropometric recovery in Phase 1 ("responders") will be randomized.

Phase 1 (Stage 1 interventions) of the study is focused on achieving anthropometric recovery. The first phase of the trial tests the effect of three types of food (RUSF, LAF, and MDSF) for the management of moderate wasting (WLZ <-2 but \geq -3, or MUAC <125 mm but \geq 115mm) on anthropometric recovery within 12 weeks of enrolment. For the study, anthropometric recovery is defined as WLZ > -2.0 or MUAC \geq 125 mm. Children will be randomized to receive either RUSF, LAF, or MDSF. Weight, length, and MUAC will be measured for all enrolled children every week during this phase to determine if anthropometric recovery has occurred.

[figure not shown]
Phase 2 (Stage 2 interventions) of the study is focused on sustaining anthropometric recovery. Children who recover from moderate wasting in phase 1 ("responders") will be randomized a second time to receive either follow-up intervention or standard care (the national standard of care for recovered children in the country). Caregivers of children randomized to the follow-up intervention group will receive a sustained recovery package or 12 weeks after the second randomization (i.e., 24 weeks after initial enrolment into phase 1) and continued counseling (once a month). The standard care group will receive no subsequent additional intervention in phase 2 from week 12 to week 24 after initial enrolment. At the end of the follow-up period, 24 weeks after enrolment, weight, length, and MUAC will be measured in all children randomized in phase 2 to assess if recovery has been sustained.

3.2 Randomization

Randomization will occur in two stages and will be stratified by study site. The first stage is for the MDSF, LAF, and RUSF interventions, and then the second randomization to the sustained recovery intervention package or standard of care will only occur among children who have anthropometric recovery by 12 weeks. We will use 'real-time' randomization for the second randomization. In the up-front approach, it is important to note that those do not recover will not receive the second-stage randomization intervention. Figure 1 below illustrates the

randomization points and then the analysis groups. Note there are 6 groups: MDSF + sustained recovery intervention (A+B), MDSF + standard (A+C), LAF + sustained recovery intervention (D+E), LAF + standard (D+F), RUSF + sustained recovery intervention (G+H), RUSF+ standard (G+I)

Figure 1. Nutrimam SMART flow and analysis groups.

First-Stage Randomization Interventions: MDSF vs LAF vs RUSF

Primary Outcomes

- 1) **12-week Anthropometric Recovery**: The outcome will be defined by reaching the anthropometric recovery at any visit time point up to 12 weeks. Anthropometric recovery will be defined as reaching a WLZ ≥ -2.0 or MUAC ≥ 125 mm based on each participant's enrollment WLZ and MUAC. If a child was enrolled in the trial due to WLZ criteria alone (WLZ <-2 but ≥ -3), then recovery will be defined by reaching a WLZ ≥ -2.0. If a child was enrolled due to MUAC criteria alone (MUAC <125 mm but ≥15mm), then recovery will be defined by reaching a MUAC ≥ 125 mm. If a child was enrolled due to both WLZ and MUAC criteria, then recovery is defined as the child reaching either WLZ ≥ -2.0 or MUAC ≥ 125 mm.
- 2) **24-week Sustained Anthropometric Recovery**: The 24-week sustained anthropometric recovery outcome will be considered a primary outcome for LAF vs RUSF and MDSF vs RUSF. 24-week sustained recovery will be considered a secondary outcome for the LAF vs MDSF comparison.

Sustained anthropometric recovery will be defined as meeting the 12-week anthropometric outcome by 12 weeks and continuing to have anthropometric recovery at 24 weeks. If a child was enrolled in the trial due to WLZ criteria alone (WLZ <-2 but \geq -3), then sustained recovery will be defined as having a WLZ \geq -2.0 by 12 weeks to meet the 12-week anthropometric recovery outcome and a WLZ \geq -2.0 at the 24-week visit. If a child was enrolled due to MUAC criteria alone (MUAC <125 mm but \geq 115mm), then sustained recovery will be defined by having a MUAC \geq 125 mm by 12 weeks for the 12-week anthropometric recovery outcome and a MUAC \geq 125 mm at the 24-week visit. If a child was enrolled due to both WLZ and MUAC criteria, then sustained recovery is defined as the child having either WLZ \geq -2.0 or MUAC \geq 125 mm by 12 weeks for the 12-week anthropometric recovery outcome and having either WLZ \geq -2.0 or MUAC \geq 125 mm at the 24-week visit.

Secondary Outcomes

- 1) Time to anthropometric recovery within the first 12 weeks (time-to-event): This will be defined as the number of days to anthropometric recovery within the first 12 weeks. The day of anthropometric recovery will be the study visit day when recovery was recorded.
- 2) Mean change in MUAC from (i) enrollment to 12 weeks and (ii) enrollment to 24 weeks: These two outcomes will be defined as the 12-week MUAC value minus the baseline MUAC value and the 24-week MUAC value minus the baseline MUAC value.
- 3) Mean change in WLZ from (i) enrollment to 12 weeks and (ii) enrollment to 24 weeks: These two outcomes will be defined as the 12-week WLZ value minus the baseline WLZ value and the 24-week WLZ value minus the baseline WLZ value.
- 4) Mean change in WAZ from (i) enrollment to 12 weeks and (ii) enrollment to 24 weeks: These two outcomes will be defined as the 12-week WAZ value minus the baseline WAZ value and the 24-week WAZ value minus the baseline WAZ value.

- 5) Mean change in LAZ from (i) enrollment to 12 weeks and (ii) enrollment to 24 weeks: These two outcomes will be defined as the 12-week LAZ value minus the baseline LAZ value and the 24-week LAZ value minus the baseline LAZ value.
- 6) Mean change in tricep skinfold thickness measurements from (i) enrollment to 12 weeks and (ii) enrollment to 24 weeks: These two outcomes will be defined as the 12-week skinfold thickness measurements value minus the baseline skinfold thickness measurements value minus the baseline skinfold thickness measurements value.
- 7) Severe acute malnutrition (SAM) (i) enrollment to 12 weeks and (ii) enrollment to 24 weeks. SAM will be defined as a WLZ < -3 z-score or MUAC <115 mm or the presence of bilateral pitting oedema.
- 8) All-cause mortality (i) enrollment to 12 weeks and (ii) enrollment to 24 weeks: Mortality will include deaths from any cause. Deaths that occur on or before day 84 of follow-up will be counted in the 12-week outcome, and all deaths that occur on or before day 168 of follow-up will be counted for the 24-week outcome.
- 9) SAM or All-cause mortality from i) enrollment to 12 weeks and (ii) enrollment to 24 weeks. This is a composite outcome of SAM or death; if SAM occurs first, the date of SAM measurement will be used to define the time of the event. SAM will be defined as a WLZ < -3 z-score or MUAC <115 mm or the presence of bilateral pitting oedema at any follow-up visit. Deaths that occur on or before day 84 of follow-up will be counted in the 12-week outcome, and all deaths that occur on or before day 168 of follow-up will be counted for the 24-week outcome.
- 10) Any hospitalization from i) enrollment to 12 weeks and (ii) enrollment to 24 weeks: Hospitalization from any cause will be defined as a stay in a health facility >24 hours.

Second-Stage Randomization Intervention: Sustained Recovery Intervention vs Standard of Care

Primary Outcome

1) Sustained anthropometric recovery will be defined as meeting the 12-week anthropometric outcome by 12 weeks and continuing to have an anthropometric recovery outcome at 24 weeks. Note that all children who are enrolled in the second-stage intervention trial will have recovered by 12 weeks due to the enrollment criteria; therefore, sustained recovery is based on the 24-week measurement.

If a child was enrolled in the trial due to WLZ criteria alone (WLZ <-2 but \geq -3), then sustained recovery will be defined as having a WLZ \geq -2.0 at 12 weeks to meet the 12-week anthropometric recovery outcome and a WLZ \geq -2.0 at the 24-week visit. If a child was enrolled due to MUAC criteria alone (MUAC <125 mm but \geq 115mm), then sustained recovery will be defined by having a MUAC \geq 125 mm by 12 weeks for the 12-week anthropometric recovery outcome and a MUAC \geq 125 mm at the 24-week visit. If a child was enrolled due to both WLZ and MUAC criteria, then sustained recovery is defined as the child having either WLZ \geq -2.0 or MUAC \geq 125 mm by 12 weeks for the 12-week anthropometric recovery outcome and having either WLZ \geq -2.0 or MUAC \geq 125 mm at the 24-week visit.

Secondary Outcomes

- 1) Mean change in MUAC from 12 weeks (randomization) to 24 weeks: This will be the 24-week MUAC value minus the 12-week MUAC value.
- 2) Mean change in WLZ from 12 weeks (randomization) to 24 weeks: This will be the 24-week WLZ value minus the 12-week WLZ value.
- 3) Mean change in WAZ from 12 weeks (randomization) to 24 weeks: This will be the 24-week WAZ value minus the 12-week WAZ value.
- 4) Mean change in LAZ from 12 weeks (randomization) to 24 weeks: This will be the 24-week LAZ value minus the 12-week LAZ value.
- 5) Mean change in tricep skinfold thickness measurements from 12 weeks (randomization) to 24 weeks: This will be the 24-week skinfold thickness measurements minus the 12-week measurement value.
- 6) Severe acute malnutrition (SAM) from 12 weeks (randomization) to 24 weeks. SAM will be defined as a WLZ < -3 z-score or MUAC <115 mm or the presence of bilateral pitting oedema.
- 7) All-cause mortality from 12 weeks (randomization) to 24 weeks. Deaths that occur on or before day 168 of follow-up will be counted for the 24-week outcome.
- 8) SAM or All-cause mortality from 12 weeks (randomization) to 24 weeks. This is a composite outcome of SAM or death; if SAM occurs first, the date of SAM measurement will be used to define the time period. SAM will be defined as a WLZ <-3 z-score or MUAC <115 mm or the presence of bilateral pitting oedema at any follow-up visit.
- 9) Any hospitalization from 12 weeks (randomization) to 24 weeks: Hospitalization from any cause will be defined as a stay in a health facility >24 hours.

Combination of First and Second Randomization Interventions

In a secondary paper, we will explore the combinations of the first and second randomization interventions, which result in 6 groups (3 first-stage randomization interventions and two second-stage randomization interventions). The study may not be adequately powered to look at the difference between the 6 combinations, and therefore, we will report these as exploratory outcomes.

We will compare MDSF + sustained recovery intervention (Figure 1 Groups A+B), MDSF + standard (A+C), LAF + sustained recovery intervention (D+E), LAF + standard (D+F), RUSF + sustained recovery intervention (G+H), RUSF+ standard (G+I). We will use weighting methods to take into account the SMART study design to address 'double counting' of the groups that did not recover at 12 weeks (Group A, Group D, Group G) (Nahum-Shani I, et al).

Exploratory Outcomes

1) 24-week sustained anthropometric recovery: Sustained anthropometric recovery is defined as meeting the anthropometric recovery by (required for the second stage randomization) and continuing to meet the recovery outcome at 24 weeks. Given that the second-stage randomization occurs after meeting the 12-week anthropometric recovery outcome, the analysis for 24-week recovery for the sustained recovery intervention vs standard of care will only utilize data from the 24-week visit. If a child was enrolled in the trial due to WLZ criteria alone (WLZ <-2 but ≥-3), then sustained recovery will be defined as a WLZ > -2.0 at the 24-week visit. If a child was enrolled due to MUAC criteria alone (MUAC

- <125 mm but \ge 115mm), then sustained recovery will be defined by having a MUAC \ge 125 mm at 24-weeks. If a child was enrolled due to both WLZ and MUAC criteria, then sustained recovery is defined as the child having either WLZ \ge -2.0 or MUAC \ge 125 mm at 24-weeks.
- 2) Mean change in MUAC from randomization to 24 weeks: This will be the 24-week MUAC value minus the randomization MUAC value.
- 3) Mean change in WLZ from randomization to 24 weeks: This will be the 24-week WLZ value minus the randomization WLZ value.
- 4) Mean change in WAZ from randomization to 24 weeks: This will be the 24-week WAZ value minus the randomization MUAC value.
- 5) Mean change in LAZ from randomization to 24 weeks: This will be the 24-week LAZ value minus the randomization LAZ value.
- 6) Mean change in skinfold thickness measurements from randomization to 24 weeks: This will be the 24-week skinfold thickness measurements minus the randomization measurement value.
- 7) Severe acute malnutrition (SAM) from randomization to 24 weeks. SAM will be defined as a WLZ < -3 z-score or MUAC <115 mm or the presence of bilateral pitting oedema.
- 8) All-cause mortality from randomization to 24 weeks (randomization) to 24 weeks. Deaths that occur on or before day 168 of follow-up will be counted for the 24-week outcome.
- 9) SAM or All-cause mortality from randomization to 24 weeks. This is a composite outcome of SAM or death; if SAM occurs first the date of SAM measurement will be used to define the time period. SAM will be defined as a WLZ < -3 z-score or MUAC <115 mm or the presence of bilateral pitting oedema at any follow-up visit. Deaths that occur on or before day 168 of follow-up will be counted for the 24-week outcome.
- 10) Any hospitalization to 24 weeks: Hospitalization from any cause will be defined as a stay in a health facility >24 hours.

3.3 Trial Sample Size

The trial sample size was based on sample size calculations for the primary outcome analyses. The sample size required for the analysis of non-inferiority of LAF as compared to RUSF on 12-week anthropometric recovery was the largest and therefore determined the overall trial sample size.

Primary Comparison #1- LAF vs RUSF on 12-week anthropometric recovery (non-inferiority): There is some evidence that justifies a non-inferiority comparison between LAF and RUSF. A meta-analysis on the management of acute malnutrition in LMICs suggests no difference in recovery from moderate wasting when standard RUSF was compared to local or homemade food, although this is considered low-quality evidence from only two studies.

The choice of non-inferiority margin was based on the judgment of clinical and public health importance of differences in the primary outcome (in our case, anthropometric recovery by 12 weeks of treatment). The investigator group and WHO staff determined that if the recovery rate with one treatment option was 60% and a non-inferiority margin of a risk difference of -5% is appropriate.

Based on assumptions of 1:1 randomization, 90% power, a one-sided α =0.025 (0.05/2 for multiple comparisons), 5% loss to follow-up/missing data, and that 60% of participants would have 12-week anthropometric recovery outcome in the RUSF and LAF arms, we would require 2,120 participants in each intervention group. As the rate-limiting randomization #1 sample size, the trial 2,120 participants are enrolled in each of the three first-stage randomization interventions, totaling 6,360 total participants in the trial.

Primary Comparison #2: MDSF vs RUSF on 12-week anthropometric recovery (**superiority**): This hypothesis is based on the evidence from a proof-of-principle study conducted in Bangladesh, which showed that MDSF is better than RUSF in promoting growth. We anticipate that 60% of enrolled children will achieve anthropometric recovery within 12 weeks of enrolment in the RUSF group (comparison group). Based on an enrollment of 2,120 per intervention arm, 1:1 randomization, an α of 0.025 (0.05/2 due to multiple comparisons), and 5% loss to follow-up/missing data, we will have 90% power to detect a relative risk of 1.09 for 12-week anthropometric recovery for MSDF as compared to RUSF.

Primary Comparison #3 MDSF vs RUSF on 24-week sustained anthropometric recovery (superiority): This hypothesis is also based on the evidence from a proof-of-principle study conducted in Bangladesh, which showed that MDSF is better than RUSF in promoting growth.

We anticipate that 40% of enrolled children in the second randomization, therefore 24% overall will achieve 24-week sustained anthropometric recovery in the RUSF group (comparison group). Based on an enrollment of 2,120 per arm, 1:1 randomization, an α of 0.025 (0.05 / 2 due to multiple comparisons), and 10% loss to follow-up/missing data, we will have 90% power to detect a relative risk of 1.21 for 24-week sustained anthropometric recovery for MSDF as compared to RUSF.

Primary Comparison #4 LAF vs RUSF on 24-week sustained anthropometric recovery (**superiority**): We believe that the LAF group could have more sustained recovery than RUSF because it has higher acceptability, lower likelihood of displacing usual diet and breastfeeding, and an easier transition to giving adequate home foods to the child in phase 2 after recovery has been achieved.

We anticipate that 40% of enrolled children in the second randomization, therefore 24% overall will achieve 24-week sustained anthropometric recovery in the RUSF group (comparison group). Based on an enrollment of 2,120 per arm, 1:1 randomization, an α of 0.025 (0.05 / 2 due to multiple comparisons), and 10% loss to follow-up/missing data, we will have 90% power to detect a relative risk of 1.21 for 24-week sustained anthropometric recovery for LAF as compared to RUSF.

Primary Comparison #5 Sustained recovery intervention vs standard of care on 24-week sustained anthropometric recovery (superiority): We believe that a follow up intervention is necessary to sustain recovery from moderate wasting, as the child has not achieved full immunological and metabolic recovery (despite anthropometric recovery) and is therefore still vulnerable and requires continued counselling and the family needs to increase intake of home foods especially where there is household food insecurity.

We assume that among participants who had 12-week anthropometric recovery (estimated 60%) and are therefore included in the second-stage randomization (n=1272 in each arm are estimated to undergo the second randomization). We assume that 45% in the standard of care group will have 24-week sustained anthropometric recovery. Based on an enrollment of 1,272 per arm, 1:1 randomization, an α = 0.05, and 5% loss to follow-up/missing data, we will have 90% power to detect a relative risk of 1.15 for 24-week sustained anthropometric recovery for the sustained recovery intervention as compared to the standard of care.

4 General Analysis Considerations

4.1 Hypothesis Testing Framework for Primary Outcomes

The study includes multiple hypothesis tests, which are presented separately for Phase 1 and Phase 2 interventions.

First Randomization Interventions: MDSF vs LAF vs RUSF

- 1. We hypothesize that supplementation with MDSF will be superior to supplementation with RUSF, in the proportion of moderately wasted children showing initial anthropometric recovery by week 12 post-enrolment (ii) and superior to RUSF on the proportion showing sustained recovery by week 24 post-enrolment.
- 2. We hypothesize that supplementation with (i) LAF will be non-inferior to supplementation with RUSF, on the proportion of moderately wasted children showing initial anthropometric recovery by week 12 post-enrolment (ii) and superior to RUSF on the proportion showing sustained recovery by week 24 post-enrolment.

Second Randomization Interventions: Sustained recovery intervention vs Standard of Care

We hypothesize that the sustained recovery intervention will result in superior rates of sustained recovery at 24 weeks.

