iv. LAF vs RUSF on 24-week sustained anthropometric recovery (superiority): This analysis will utilize data from visits during the first 12 weeks in addition to the 24-week visit. Sustained anthropometric recovery is defined by 12-week anthropometric recovery and continued recovery at the 24-week visit.

If a participant does not complete any follow-up visits at or before the 12-week visit (no 12-week follow-up data), they will be excluded from the analysis (complete case). Participants who reached anthropometric recovery at 12 weeks but do not have anthropometric data at 24 weeks (loss to follow-up/missing data, death, withdrawal) will also be excluded from the analysis (complete case). Participants who did not meet 12-week anthropometric recovery will be analyzed as not having met 24-week sustained

recovery, regardless of their completion of the 24-week visit, as by definition they are known to not have met the sustained recovery endpoint.

We will report the proportion of participants who reached sustained anthropometric recovery at 24 weeks by intervention arm. We will use a log-binomial regression model to present the relative risk (RR) of 24-week sustained anthropometric recovery for the LAF arm compared to the RUSF arm. Due to stratified randomization by study site, we will include a fixed effect for the study site in the model. We will present the relative risk, 97.5% confidence intervals, and a p-value <0.025 will be considered statistically significant (to account for multiple comparisons)

v. Sustained recovery intervention vs standard of care on 24-week sustained anthropometric recovery (superiority):

Given that the second randomization occurs after meeting the 12-week anthropometric outcome, the analysis for 24-week sustained recovery for sustained recovery intervention vs standard of care will only utilize data from the 24-week visit to define the outcome for this comparison.

We will report the proportion of participants who reached sustained anthropometric recovery at 24 weeks by intervention arm. We will use a log-binomial regression model to present the relative risk (RR) of 24-week sustained anthropometric recovery for the sustained recovery intervention as compared to the standard of care arms. Due to stratified randomization by study site, we will include a fixed effect for the study site in the model. We will present the relative risk, 95% confidence intervals, and a p-value <0.05 will be considered statistically significant.

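### Second-stage entry needs recovery at only one visit by week 12, so a child below threshold again at week 12 can be scored as sustained; the SAP also mixes *at* and *by* 12 weeks

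*SAP*

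**What the plan says.** **Recovery rule.** SAP section 3.2 (first-stage primary outcome 1) defines 12-week recovery as reaching the threshold at "any visit time point up to 12 weeks". Section 3.1 has anthropometry taken weekly in Phase 1. No confirming visit is required.

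**Second-stage entry.** Section 3.2 says the second randomisation "will only occur among children who have anthropometric recovery by 12 weeks". Section 3.1 describes entrants as "only children who reached the anthropometric recovery in Phase 1", and section 4.2 defines the second-stage analysis population in the same sense.

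**Timing.** Section 3.1: "The second randomization stage occurs after 12 weeks and is referred to as 'Phase 2". The second-stage secondary outcomes in section 3.2 treat week 12 as the randomisation point, for example "Mean change in WLZ from 12 weeks (randomization) to 24 weeks".

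**Second-stage primary outcome.** Section 3.2 bases it on the week-24 measurement, with the justification "Note that all children who are enrolled in the second-stage intervention trial will have recovered by 12 weeks due to the enrollment criteria". Section 5.2 (v) repeats that the analysis "will only utilize data from the 24-week visit to define the outcome for this comparison".

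**Exception.** The detailed second-stage definition in section 3.2 requires of WLZ-only children a WLZ of at least -"2.0 at 12 weeks to meet the 12-week anthropometric recovery outcome". In the same paragraph, MUAC-only and both-criteria children need recovery only *by* 12 weeks.

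**The concern.** Phase 2 is described in section 3.1 as being about sustaining recovery. Between a first crossing in the early weeks and the second randomisation there can be many weeks in which a child falls back below the threshold. Nothing in the SAP removes such a child from the second randomisation, and the outcome ignores the week-12 reading. For that child, being above threshold at week 24 means recovery was regained, yet it is recorded as sustained.

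Two things are at stake. The first is the meaning of the relative risk in comparison v (package versus standard care, section 5.2 v): it may average an effect on keeping recovery and an effect on regaining it. The second is reproducibility of a primary endpoint: with *at* in one place and *by* in others, two programmers following the SAP could score the same child differently.

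**Working it through.** **1. The wordings side by side (SAP)**

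| Place | Children | Week-12 condition |
|---|---|---|
| 3.2, first-stage sustained recovery | all entry groups | *by* 12 weeks |
| 3.2, second-stage primary outcome, opening text | all | *by* 12 weeks; week 24 decides |
| 3.2, second-stage detailed definition | WLZ-only | *at* 12 weeks |
| 3.2, second-stage detailed definition | MUAC-only; both criteria | *by* 12 weeks |
| 3.2, combined-stage exploratory outcome | all | scored on week 24 only |
| 5.2 (iii) | all | *at* in the missing-data exclusion, *by* in the rule for failures |
| 5.2 (iv) | all | *at* in the missing-data exclusion, 12-week recovery met or not in the rule for failures |
| 5.2 (v) | all re-randomised | none; week 24 only |

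**2. One course run through the rules.** Take a child recovered at week 6, below threshold at week 12 and above it at week 24.
- First-stage definition: sustained, for every entry group.
- Second-stage detailed definition: not sustained if WLZ-only, sustained if MUAC-only or both.
- Section 5.2 (v): sustained, for every entry group.

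If the week-24 visit is missing, then on the literal wording of section 5.2 (iii) this child is neither excluded (not recovered *at* week 12) nor a failure (recovered *by* week 12).

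**3. The plan's own power figure.** Inputs from section 3.3, Primary Comparison #5: 1,272 per arm, 5% loss, control rate p0 = 0.45, RR 1.15, α = 0.05 (taken as two-sided).

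n = 1,272 × 0.95 = 1,208.4; p1 = 0.45 × 1.15 = 0.5175; p̄ = 0.48375.

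Power = Φ{[(p1 − p0)√n − 1.96√(2p̄(1 − p̄))] / √(p0(1 − p0) + p1(1 − p1))} = Φ{(2.346 − 1.385)/0.705} = Φ(1.363) = 91%.

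The smallest RR detectable with 90% power is 1.146. The stated 90% at RR 1.15 reproduces.

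**4. How the pooled RR would move.** Let f be the share of re-randomised children below threshold at week 12 and q the week-24 success rate of such children under standard care. The SAP gives neither. The pooled RR is a weighted average of the RR in those children and the RR in the rest, with weight w = f × q / 0.45 on the former.

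Suppose the RR is 1.15 in children still recovered and 1 in the others. The pooled RR is then 1.15 − 0.15w:
- f = 10%, q = 20% to 45%: w = 0.044 to 0.10, RR = 1.143 to 1.135.
- f = 20%, q = 20% to 45%: w = 0.089 to 0.20, RR = 1.137 to 1.120.

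If the package worked better in children who had fallen back, the pooled RR would exceed 1.15. The direction is therefore open.

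**5. Power of an analysis restricted to children recovered at week 12.** Same formula, with n = N × (1 − f) × 0.95 and the 45% control rate kept. Section 3.3 states N = 1,272, which is 60% of 2,120. Sixty per cent of all 6,360 children, halved, is 1,908; both are shown.

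| f (assumed) | Randomised per arm, from 1,272 | Power | Randomised per arm, from 1,908 | Power |
|---|---|---|---|---|
| 10% | 1,145 | 88% | 1,717 | 97% |
| 20% | 1,018 | 84% | 1,526 | 95% |
| 30% | 890 | 79% | 1,336 | 93% |

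**The case against.** The strongest reply is that the any-visit rule is deliberate. It is stated outright for the primary outcome, and *by* 12 weeks recurs through section 3.2. Under that definition the sentence about second-stage entrants is true, and comparison v is an intention-to-treat effect in responders as this design defines them. The single *at* may be a slip: its own clause refers back to the 12-week outcome, which is any-visit, and section 5.2 (v) never uses it. The second-stage continuous outcomes already start from the week-12 value and adjust for baseline (sections 3.2 and 5.3).

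Much of this stands. It shows that the comparison is valid and the rule intended. It does not show that a week-24 reading alone distinguishes sustained from regained recovery, and a probable slip in a primary endpoint definition still has to be corrected. Week-12 status is not among the five effect modifiers in section 5.6.

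The mention of real-time randomisation in section 3.2 could be read as randomising at first recovery, which would remove the gap. However, section 3.1 puts the second randomisation after 12 weeks and equates 12 weeks after it with week 24, and the secondary outcomes label week 12 as randomisation.

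Four stronger readings do not hold:
- **Objective 3 is not tested.** The objective (section 2.2) does not restrict itself to children recovered at week 12.
- **Children with severe acute malnutrition at week 12 are re-randomised.** That depends on enrolment criteria and clinical handling that a protocol may set and that are not shown here.
- **A count of affected children can be modelled.** A model of linear growth plus measurement error counts readings scattered around the threshold. It contains no relapse.
- **Sustained recovery must be redefined as recovered at both weeks 12 and 24.** That is a debatable change to a primary endpoint. In comparison v it would make every child below threshold at week 12 a failure in both arms.

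**Conclusion.** The point holds as a matter of definition and interpretation. As the SAP is written, children below threshold at week 12 can enter the second randomisation and be scored as sustained, so comparison v can combine maintained and regained recovery. The week-12 requirement for WLZ-only children contradicts the rest of the SAP and would score identical courses differently by entry criterion.

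The randomised comparison is not biased by this. The SAP gives no share of responders below threshold at week 12, so the size is unknown. The shares of 10% to 30% used above are assumptions, as are the values of q and of the effect in children who had fallen back. A protocol entry rule requiring recovery at the week-12 visit would close the gap; the SAP describes entry only as recovery by 12 weeks.

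**What to change.** 1. State one week-12 rule for all three entry groups, and use it in every sustained-recovery definition in section 3.2 (first-stage, second-stage and combined) and in section 5.2 (iii) to (v), including the missing-data rules. Who should enter Phase 2 is for the trial team to reconcile.
2. For comparison v, keep all re-randomised children as the primary intention-to-treat set and add recovery status at the week-12 visit as a covariate. It is known before the second randomisation, so adjusting for it is legitimate.
3. Pre-specify a supportive analysis of the same outcome in children recovered at the week-12 visit. It is still a randomised comparison, for the same reason. State how a child with a missed week-12 visit is handled in both the covariate and this subset.

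**Cost.** Wording changes, one covariate and one extra model, using measurements already planned. The supportive analysis has fewer children and less power, as tabulated under the stated assumptions. The primary endpoints of comparisons iii and iv need only consistent wording, not a new definition.
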